Mu wave suppression paradigm: If subjects agree to participate in this sub-study, the informed consent for EEG collection will be obtained prior to any EEG procedures. EEG waves will be recorded over 32-sites using a standard 32-electrode cap with the Biosemi system (9), while subjects are watching 60-80 second videos. The videos will consist of experimental conditions (point light animations of biological and non-biological motion, scrambled condition) and baseline condition (2 moving balls). All videos will be presented twice, using Presentation software (10). Data from both trials will be combined prior to analysis. Filters will be set to automatically identify and block any segments with eye movements and body movements (using +/- 40 microvolt deviations). Data will only be analyzed if there is at least 2 minutes of clean EEG per condition. For each segment, integrated power in the 8–13 Hz range will be computed using a Fast Fourier Transform. Mu suppression will be calculated for central (C3, Cz and C4) and occipital (O1 and O2) sites using the equation: Mu suppression = log10 (mu power of experimental condition/ mu power of ball condition). Occipital site electrical discharges will be recorded, integrated for power and compared between groups to determine if posterior alpha activity is causing differences across conditions.

STUDY PROCEDURES

Visit	Screen	Baseline	Midweek	3	4	5	6	7	8/ET
Week	-1	0	0	1	2	3	4	5	6
Days	-7 to -1	0	3/4	7	14	21	28	35	42
General Procedures									
Informed Consent	Х								
Assess Inclusion/Exclusion	Х	Х		Χ	Х	Х	Х	Х	Х
Medical History	Х								
Physical Exam	Х								
SCID/Psychiatric History	Х								
Urine Drug Screen ^b	Х								
Urine Pregnancy Screen ^c	Х	Х							
Vital signs/ weight	Х	Х		Χ	Χ	Х	Х	Х	Х
Blood chemistryd/Urine osmolality	Х								Х
Oxytocin Levels ^e		XX							Х
EEG	XX								Х

Clinician-Rated Scales									
PANSS ^f	(x)	Х		Х	Х	Х	Х	Х	Х
HAM-A/ CDSS/ CGI:S ⁹ /									
CGI:I/ GAF		Х		Х	Χ	Х	Х	Х	Х
Cognitive tests (CMINDS® and									Х
MSCEIT [™] ME) ^h	Х	Х							
Patient-Rated Scales									
CTQ	Х								
TSQM		Х		Х	Х	Х	Х	Х	Х
PTS/ SPIN/ ASEX ⁱ /									
ER-40/ ECR		XX		Х	Х	Х	Х	Χ	Х
Other Procedures									
Mid-Week Safety Call ^j			Х						
Dispense study drug		Х		Х	Х	Х	Х	Х	
Single Challenge Dose ^k	Х								
Concomitant Meds		Х	Х	Х	Х	Х	Х	Х	Х
Adverse Events		Х	Х	Х	Х	Х	Χ	Х	Χ
1-hr safety monitoring following in-									
clinic dose		Х							

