^aScreening procedures can be done over a week period if needed to complete all procedures such as confirmation of diagnosis. The screening and baseline visits can occur on the same day.

^cPremenopausal women will be queried regarding their menstrual cycles and data correlated with clinical findings.Patients are instructed to use a medically accepted form of birth control through their study participation, and are also questioned about their birth control method at each visit. If a pregnancy is suspected at any time during the study, the patient will be asked to complete a urine pregnancy test.

^eOxytocin Levels will be collected via saliva and blood draw twice during the Baseline Visit. One blood draw and passive drool will be collected at the beginning of the visit (pre-dose) and a second blood draw and passive drool collection will be taken 30 minutes after the in-clinic dose. The third Oxytocin level will be taken at the patient's last visit (either Visit 8 at the conclusion of the protocol or the Early Termination visit).

^f PANSS must be done at baseline, but it may be completed at screening in addition at the discretion of the investigator if he feels that the subject may not met entry criteria

⁹The CGI-S will be completed twice at the Baseline Visit, once prior to dosing and a second time at least 50 minutes after the in-clinic dose of the study drug or placebo.

^b In addition to Visit 1, an optional urine drug screen or blood chemistry may be performed at any point during the study at the discretion of the Principal Investigator or study coordinators if it is suspected the subject is not abstaining from illegal substances or have general health concerns.

^d Basic Metabolic Panel includes Glucose, BUN, Creatinine, Bicarbonate, Chloride, Sodium, Potassium, Calcium, osmolality

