- If the volunteer is a woman capable of having children, a urine test will be done to ensure she is not pregnant
- Give a urine sample for testing to make sure there are no illegal or controlled substances in his/her body. The results of any urine drug screen will remain confidential and be disclosed only as required by law
- Blood draw (about one teaspoon or 5 mL) and urine sample will be collected that will include standard tests to make sure volunteers are healthy
- Be asked questions about health and any current illnesses or medications (including over-the-counter medications, herbal remedies, alcohol consumption, and substances of abuse).
 Be asked a series of questions about how s/he was feeling within the past few weeks such as whether there were anxious feelings, feelings of depression or difficulty concentrating. The volunteer will also possibly be asked about symptoms that are commonly associated with schizophrenia using a clinical interview called the SCI-PANSS (Structured Clinical Interview Positive and Negative Syndrome Scale).

The SCI-PANSS will be completed at the discretion of the investigator if he feels that the subject may not met entry criteria

- Complete a series of activities which will be used to measure process of thought called the CMINDS® and MSCEIT™ ME
- Premenopausal women will be queried regarding their menstrual cycles and data correlated with clinical findings
- Once all inclusion/exclusion criteria have been met subjects will have a baseline EEG performed
- Subsequently subjects will receive a, one time, challenge dose of 24 or 48 IU oxytocin followed by the EEG paradigm

Visit 2-Baseline (approximately 2 hours)

During Visit 2 – Baseline, the volunteer will:

- Have weight, pulse and blood pressure measured
- Be asked questions about health and any current illnesses or medications (including over-the-counter medications, herbal remedies, alcohol consumption, and substances of abuse)
- Be asked a series of questions about how s/he was feeling within the past few weeks such as whether
 there were anxious feelings, feelings of depression or difficulty concentrating. The volunteer will also be
 asked about symptoms that are commonly associated with schizophrenia using a clinical interview called
 the SCI-PANSS (Structured Clinical Interview Positive and Negative Syndrome Scale)
- Complete a series of activities which will be used to measure process of thought called the CMINDS® and MSCEIT™ ME

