- Complete a questionnaire about symptoms of paranoia and sexual functioning
- Complete a test onability to recognize emotions called the Penn Emotion Recognition Test (ER-40).

Additionally at Visit 8 (week 6 or Early Termination);

- Complete a series of activities which will be used to measure process of thought called the CMINDS® and MSCEIT™ ME
- Have an additional blood sample taken (about 1 tablespoon) to monitor study drug levels in the blood
- EEG paradigm will be conducted

Follow Up Call

The volunteer will be asked to contact the study site one week after the last study drug dose to report taking any new medications or any unusual experiences since stopping the study drug.

Administration and dispensing of the study medication:

Except the one time challenge dose, this is a double-blind study, participants will be randomized to receive one of three possible intranasal study medications adjunctive to their antipsychotics: oxytocin 84 IU, oxytocin 168 IU or placebo (vehicle without oxytocin). Randomization will be performed stratifying gender groups, type of antipsychotic (typical versus atypical) and severity of symptoms based upon PANSS score (<90 versus >90) so that gender, symptom severity and antipsychotic type are distributed relatively evenly across treatment groups. Bottles containing placebo or two different concentrations of oxytocin will be formulated (See Study Drug Formulation below) so that the concentration of oxytocin in the high dose (168 IU) will be double that of the low dose (84 IU). All subjects will be instructed to spray 7 pumps of the spray bottle (one in each nostril, alternating nostrils) to achieve correct dose in the morning and again in the afternoon. Subjects will be given enough study drug at the time of the visit to last until the next visit with extra to cover approximately three additional days. Each pump bottle has 5 ml (300 IU) which is enough for 2.5 days of study drug. Therefore, subjects will be given one spray bottle supply at the time of each visit. The weight of each bottle will be recorded prior to dispensing. After all procedures are performed on baseline visit and study drug is randomly assigned, a dose of the study drug will be taken at the study site, in the presence of a staff member to insure correct administration.

Study Drug Compliance

- 1. Subjects will be instructed on proper use of the nasal device from study staff.

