14. POTENTIAL RISKS

All medications have side effects and some of these can be unexpected and unforeseen. Subjects will be closely monitored throughout the trial duration and subjects will be provided emergency contact numbers to ensure 24-hour monitoring.

Nasal Inhalation Oxytocin

The FDA (see appended letter) notes "lack of safety concerns" associated with the clinical use of oxytocin despite ", the length of marketing history of this product in the U.S., the continued availability of the injectable oxytocin in the US and the IN form outside the US" A drug insert provided with IN nasal oxytocin in Europe where it continues to be marketed for lactation lists the following risks; painful uterine contracts; in rare occasions, allergic skin reactions, nausea or headache. Several published studies have used various doses (18- 360 IU) of IN oxytocin administered once to more than a week (e.g. Ansseau et al, 1987; Epperson 1996; Fehm-Wolfsdorf et al, 1988; Westenberg, 1992; Kosfeld et al 2005; Ruis et al, 1981; Heinrichs et al 2003; Fewtrell et al 2005; Bruins et al 1992.) Most studies do not report any adverse effects. One case (Ansseau et al, 87) of a patient developing reversible memory loss, psychosis, and a decrease in plasma sodium and osmolality is reported which is consistent with a picture of SIADH. Some studies reported decreases in verbal recall and memory whereas others did not find this. Other rare mild and transient effects were reported in some studies including, dry mouth, mild dizziness, mild headache, and mild nasal irritation. No effect on blood pressure has been noted.

Risks of Blood Draw

During the study, blood will be drawn 8 times for chemistry basic panel. Some problems from this are: pain, bleeding, bruising, swelling, dizziness, fainting, in rare cases, infection at the insertion site.

Additional Risks

Since this is an experimental treatment there may be some unknown risks that are currently unforeseeable. Subjects will be informed of any significant new findings.

Symptoms of schizophrenia may not improve or may worsen. There is also the possibility that there may be unforeseen risks associated with this test article, which are not yet known.

Allergy Risks

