15. RISK MANAGEMENT PROCEDURES AND ADEQUACY OF RESOURCES

A staff that is highly qualified in the assessment and treatment of schizophrenia in adults will closely monitor subjects in this study. This monitoring includes the frequent periodic assessments involved in the study protocol, which occur at intervals of 1 week long. Study drug will be administered on site following both baseline visits. Mid-week calls are set up following both baseline visits along with a study treatment follow up visit. In addition, subjects will be monitored throughout the study for any adverse events. Subjects will be instructed by the Investigator to report the occurrence of any adverse events immediately. At the beginning of each treatment period, the Investigator will query the subjects, in a generalized fashion, whether any clinical adverse events have occurred since the last visit. Any serious or unexpected event, including death due to any cause, whether or not related to the study drug or procedures, will be reported to the UCSD HRPP within 10 days.

After a thorough literature search was performed and confirmed the relative safety profile of this drug, the following additional safety measures were added in an attempt to be thorough.

Biological safety measures include blood chemistry and urine osmolality to monitor for SIADH. These tests will be done at screening and at every visit after randomization. In addition a blood metabolic assay (glucose, liver enzymes) will be conducted at each visit.

If any clinical worsening or serious adverse event is detected during the course of the trial that cannot be managed by a dose adjustment, the subjects will be discontinued from the protocol.

It is my intention to provide contact information for study staff to the subjects and reiterate this information at the time of each visit. Contact information for PI, and Drs. [name] and [name], are listed on the diary form that will be provided to the subject at each visit. Study subjects will be encouraged, as documented in the consent and on the separate diary form, to contact the study team with medical concerns, reactions, and experiences. Subjects will be given a diary form to complete upon each use for administrations that are done between site visits. This diary form includes 24 hour emergency contact information (including PI, sub-Is and study staff), nearest emergency department from subject's residence and concomitant medication diary.

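### The schedule table has safety chemistry and urine osmolality at 2 time points; the risk sections imply 7 or 8, and liver enzymes have no scheduled place

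*Combined protocol and SAP*

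**What the plan says.** Four places in the combined protocol and SAP bear on when safety chemistry is taken.

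- **Section 15 (Risk Management Procedures).** Blood chemistry and urine osmolality are named as the biological measures for SIADH: "These tests will be done at screening and at every visit after randomization". The next sentence adds a blood assay of glucose and liver enzymes at each visit.
- **Section 14 (Potential Risks), blood-draw paragraph.** "During the study, blood will be drawn 8 times for chemistry basic panel". Urine osmolality is not mentioned.
- **Section 9, Study Procedures table and footnotes.** The row "Blood chemistryd/Urine osmolality" (the d is a footnote mark) has a mark under Screen and a mark under Visit 8/ET. Footnote d lists the panel, which contains glucose, sodium and osmolality but no liver enzymes. Footnote b adds that "an optional urine drug screen or blood chemistry may be performed at any point during the study", at the discretion of the principal investigator or coordinators.
- **Section 9, Study Procedure Details (visit lists).** At Visit 1, blood and a "urine sample will be collected that will include standard tests to make sure volunteers are healthy". The extra item at Visit 8 is "Have an additional blood sample taken (about 1 tablespoon) to monitor study drug levels in the blood". No list after Visit 1 names safety chemistry.

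The hazard is the protocol's own. Section 14 describes a published case in which "a decrease in plasma sodium and osmolality is reported which is consistent with a picture of SIADH".

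**The concern.** Site staff usually work from the schedule table, whereas someone judging the risk of the trial reads the risk sections. Here the two describe different monitoring. A reader of Section 15 would expect a sodium and osmolality check every week on treatment; a coordinator following the table would take none between screening and the final visit. At stake is whether a fall in sodium without symptoms would be looked for during weeks 1 to 5. If more than one site takes part, as Specific Aim 1 envisages, sites could also follow different schedules in good faith, and the amount of laboratory safety data per subject would then differ by site.

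**Working it through.** This is a count of scheduled time points in each source; no power or sample-size formula applies.

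**Inputs.** Visits and days are from the table header: Screen (day -7 to -1), Baseline (day 0), then Visits 3, 4, 5, 6, 7 and 8 on days 7, 14, 21, 28, 35 and 42. Randomization is at Visit 2, the baseline visit (Study Procedure Details).

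**Is the table row intact?** The row fills nine cells, with marks in the first and last. The vital-signs row just above carries a mark at every clinic visit, so the columns came through properly and lost marks are an unlikely explanation.

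**Counts of scheduled chemistry**

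| Source | Time points | Count |
|---|---|---|
| Section 9 table | Screen, Visit 8/ET | 2 |
| Section 15, SIADH tests | Screen + Visits 3-8 | 1 + 6 = 7 |
| Section 15, glucose and liver enzymes | Visits 1-8 | 8 |
| Section 14, chemistry basic panel | stated | 8 |

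**Can the stated 8 be reproduced?**
- From Section 15, yes, in two ways: count the baseline visit with the SIADH tests (1 + 1 + 6 = 8), or use the assay at each visit (Visits 1 to 8 = 8). Footnote a notes that "The screening and baseline visits can occur on the same day", which would leave 7 separate visit days.
- From the table, no. Even counting every scheduled blood draw, including oxytocin levels: screening chemistry 1 + baseline oxytocin 2 (before and 30 minutes after the dose) + Visit 8 chemistry and oxytocin, 1 if combined or 2 if separate. The total is 4 to 5, against 8.

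**Checks on treatment, for a completer**
- Table: chemistry after randomization at Visit 8 only = 1. Nothing at Visits 3, 4, 5, 6 and 7 = 5 visits without a scheduled value.
- Section 15: Visits 3 to 8 = 6 values, 7 days apart.
- Gap between the two table values: 42 - (-7) = 49 days at most; 42 - (-1) = 43 days if screening is on day -1; 42 days if screening and baseline share a day. The range is 42 to 49 days.

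**Liver enzymes.** Table rows: 0. Footnote d panel: not listed. Section 15: each visit. Glucose is in the panel, but the table schedules that panel only twice.

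**The case against.** The best defence is that the sources are nested. The table's two time points lie within Section 15's seven, an unmarked cell is not a prohibition, and footnote b permits chemistry at any time. A site could satisfy all of them by testing at every visit, so it would be wrong to say that staff cannot comply. That much stands. But footnote b makes the extra tests optional, while Section 15 states them as scheduled, so a site following the table exactly would still omit them.

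Two stronger readings are tempting and are not supported.

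- **The visit lists as a further schedule, with safety tests at screening only.** The lists are plain-language summaries and are not exhaustive: compared with the table, they also leave out the CTQ, the TSQM and the baseline pregnancy test. Their silence on Visit 8 chemistry is an omission to correct. Treating it as a schedule would also imply that no end-of-treatment laboratory value exists, whereas both the table and Section 15 provide one.
- **7 against 8 as a serious conflict of its own.** Section 15's assay at each visit gives 8 and largely explains the count in Section 14. The panel names differ, so the match is not exact, but only the status of the baseline visit needs stating.

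It is also fair to say that the table does not leave subjects unobserved. Early leavers have chemistry at the ET visit, adverse events are reviewed weekly, subjects have 24-hour contact, and discretionary testing is available.

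**Conclusion.** The contradiction is real and must be fixed. Its size is 2 scheduled time points against 7 or 8, or, for a completer, five weekly on-treatment checks that one section promises and the table does not contain. Liver enzymes are a second, smaller conflict: promised at each visit and scheduled nowhere.

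The harm is conditional. It arises if staff follow the table, do not use the discretionary option, and a subject's sodium falls between visits without signs that adverse-event review would pick up. A reader might infer that SIADH would go unmonitored or that the trial's results are compromised; the documents support neither. The primary PANSS analysis uses none of these measurements.

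The conclusion assumes that visits after randomization means Visits 3 to 8. Counting baseline as well moves 7 to 8 and changes nothing else. The documents do not show which schedule was intended, and this review takes no position on that.

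**What to change.** Reconcile the Section 9 table and footnotes, the Section 14 draw count and Section 15 so that all give:

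1. one schedule for blood chemistry and urine osmolality;
2. one draw count, stating whether the baseline visit is included;
3. one statement on whether and when liver enzymes are measured, with a table row or an entry in footnote d if they are.

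Then bring the visit lists for Visit 2 and Visits 3 to 8 into line, including any chemistry and urine sample at Visit 8. The clinical team decides which schedule applies.

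**Cost if the table is confirmed:** edits to Sections 14 and 15 and to the Visit 8 list, with no added procedure.

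**Cost if Section 15 is confirmed:** chemistry and urine samples at Visits 3 to 7, where the table now has no blood draw. That is 5 per completer, or 5 x 72 = 360 draws if all of about 72 subjects complete. The plan also mentions 71 and 80 subjects, which would give 355 and 400. Keeping an assay at each visit adds one at baseline, where blood is already drawn for oxytocin levels. Assay costs come on top and are not given in the documents.

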16. PRIVACY AND CONFIDENTIALITY CONSIDERATIONS INCLUDING DATA ACCESS AND MANAGEMENT

In order to maximize patient privacy, all consenting will be done in a private room in an office, where the participant can ask questions without feeling uncomfortable or embarrassed. If and when the study doctor needs to perform a physical exam, the patient will be provided with a private room to undress and dress. While receiving the physical exam the only person who will be in the room other than the patient will be the study doctor conducting the exam. If, however, the study doctor is of the opposite gender to the patient, a staff member of the same gender as the patient will also be in the room during the physical exam.

Confidentiality will be maintained through physical and electronic security measures. The study office where patient files are maintained is kept locked, and only authorized research staff are allowed access. Research participant information stored electronically is maintained on computers with appropriate UCSD approved security firewalls, password protection, and other data storage safety measures.

Once a subject has enrolled in the study, a sequential Subject Identification (SubID) Number will be assigned. The SubID number is to be recorded on all study documents and will link the study treatment and the study documents to the subject's name and medical record. To maintain confidentiality, the subject's name will not be recorded on any study document other than the informed consent.

Patient's blood or urine sample will be tested for certain types of drugs (known as controlled substances in the United States) that may affect behavior and that may be regulated by law. If test results show that they have taken these types of drugs, they will be notified. The results of this test will be kept confidential and disclosed only as required by law. It is possible that positive drug screen results may become known outside of the research setting. If this information was disclosed, it could potentially jeopardize their ability to get a job or insurance.

